12.1 Institutional Review Board (IRB) approval

12.2 Ethical and scientific conduct of the clinical research study

The clinical research study will be conducted in accordance with the current IRB-approved clinical protocol; ICH GCP Guidelines adopted by the FDA; and relevant policies, requirements, and regulations of the CCRS, ICMR.

12.3 Subject informed consent:

The Sponsor-Investigator will make certain that an appropriate informed consent process is in place to ensure that potential research subjects, or their authorized representatives are fully informed about the nature and objectives of the clinical study, the potential risks and benefits of study participation and their rights as research subjects. The Sponsor-Investigator or a sub-investigator(s) designated by the Sponsor-Investigator will obtain the written, signed informed consent of each subject, or the subject's authorized representative, prior to performing any study-specific procedures on the subject. The date and time the subject, or the subject's authorized representative, signs the informed consent form and a narrative of the issues discussed during the informed

consent process will be documented in the subject's case history. The Sponsor-Investigator will retain the original copy of the signed informed consent form and a copy will be provided to the subject, or to the subject's authorized representative.

The Sponsor-Investigator shall make certain appropriate processes and procedures are in place to ensure that ongoing questions and concerns of enrolled subjects are adequately addressed and that the subjects are informed of any new information that may affect their decision to continue participation in the clinical study. In the event of substantial changes to the clinical study or the risk-to-benefit ratio of study participation, the Sponsor-Investigator will obtain the informed consent of enrolled subjects for continued participation in the clinical study.

14. References:

1. Yugi vaidya chinthamani, I Edition, Pub:, Year:, Page no 240, poem-739,
2. Smith's General Urology, 17th Edition, Page no.348-374
3. Quality control standards for certain Siddha formulations Published by CCRAS, 1991, Page 34
4. [Neelima Dhingra](#) & [Deepak Bhagwat](#), Indian Journal of Pharmacology, Benign prostatic hyperplasia:An overview of existing treatment, Year 2011, Volume 43, Issue 1, Page 6-12
5. American Urological Association Guideline, Management of Benign Prostatic Hyperplasia, Revised 2010,

6. Post void dribbling Present Absent Duration-----

II.Irritative symptoms:

7. Urgency Present Absent Duration--

8. Frequency Present Absent Duration-----

[figure not shown]
[figure not shown]
-

9. Nocturia Present Absent Duration-

Nei kuri examination:

Before Treatment
Treatment

After

Description:

Udaliyal:

S.No	Vatham	Pitham	Kabam
1.	Lean built	Medium built	Stout / Well built
2.	Less strength	Medium strength	Good strength
3.	Dry body	Excessive sweating	Oily body
4.	Dry & Dark skin	Pinkish or yellowish skin	Fair, Soft & smooth skin
5.	Scanty and brown hair	Early graying & baldness	Black & thick hair
6.	Fickle minded	Short tempered	Steady & patient
7.	Irregular appetite & thirst	Excessive appetite & thirst	Normal appetite & thirst
8.	Constipating tendency	Frequent & large stools	Normal steady bowel
9.	Disturbed sleep	Average sleep	Sound deep sleep

Vali

Azhal

Iyyam

Thontham

Udaliyal: _____

Date:

Signature of Research Official

PROTOCOL FOR VALIDATION OF XXX IN
PURASTHA KOLAPERUKKAM (BENIGN PROSTATIC HYPERPLASIA)

FORM III – CLINICAL ASSESSMENT FORM

Date	Day	Weight	BP	Clinical Data	IPSS	Sign of Research official
	0					
	I- Visit 15 th day					
	II-Visit 30 th day					
	III- Visit 45 th day					
	IV- Visit 60 th day					
	V – Visit 75 th day					
	VI- Visit 90 th day					

DRUG COMPLIANCE REPORT FORM– 1st Visit

[To be filled by study participant]

1. Code No.
2. Subject No. _____ Name _____
3. Trial commenced on:
4. Drug: _____

Instructions:

- a) Write the date and put “tick” mark after taking the appropriate dose.
- b) Put “X” mark if you do not take the medicine.
- c) Write if any adverse events found during intake of medicine.
- d) Please return the unused medicine along with the drug compliance report duly filled.

S.No	Date	Dose 1 (after breakfast)	Please enter the time	Dose 2 (after dinner)	Please enter the time
1.					
2.					
3.					
4.					
5.					
6.					
7.					
8.					
9.					
10.					
11.					
12.					
13.					
14.					
15.					

Next visit may be on..... (Date and time is to be filled
by the Investigator)

**Signature of the patient
research official**

Signature of the

Assessment form – Visit I

INTERNATIONAL PROSTATE SYMPTOM SCORE SHEET							
[name]:		Address:					
Patient Name:		Address:					
Date:							
Age Group:	40-49 	50-59 					
	60-69 	70+ 					
	Not at all	Less than 1 time in 5	Less than half the time	About half the time	More than half the time	Almost always	Your score
1. INCOMPLETE EMPTYING Over the past month, how often have you had a sensation of not emptying your bladder completely after you finished urinating?	0	1	2	3	4	5	
2. FREQUENCY Over the past month, how often have you had to urinate again less than two hours after you finished urinating?	0	1	2	3	4	5	
3. INTERMITTENCY Over the past month, how often have you found you stopped and started several times when you urinated?	0	1	2	3	4	5	
4. URGENCY Over the past month, how often have you found it difficult to postpone urination?	0	1	2	3	4	5	
5. WEAK STREAM Over the past month, how often have you had a weak urinary stream?	0	1	2	3	4	5	
6. STRAINING Over the past month, how often have you had to push or strain to begin urination?	0	1	2	3	4	5	
7. NOCTURIA Over the past month, how many times did you most typically get up to urinate from the time you went to bed at night until the time you got up in the morning?	None 0	1 time 1	2 times 2	3 times 3	4 times 4	5 or more times 5	
Which of the above do you regard as most troublesome [1-7] _____							
TOTAL PROSTATE SYMPTOM SCORE _____							
	Delighted	Pleased	Mostly satisfied	Mixed - satisfied and dissatisfied	Mostly dissatisfied	Unhappy	Terrible
QUALITY OF LIFE DUE TO URINARY SYMPTOMS If you were to spend the rest of your life with your urinary condition just the way it is now, how would you feel about that? (tick one).	0	1	2	3	4	5	6

Date:

Signature of the
Research Official

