- Clinical evidence of any of the bladder or urinary tract conditions, which may affect lower urinary tract symptom at initiation
- Patient having a post void residual urine volume 350 cc.
- Patients who have participated in any drug study during the past 3 months
- Any condition which are likely to hinder the compliance with the protocol.

5. Study drug(s):

Arm 1: xxx

(In reference text book the dosage is mentioned as 488 mg, but in this clinical study the dosage is fixed as 100 mg)

[This is given along with milk and administered two times a day after food.]

Arm 2: xxx

[To 20 gram of powder 150 ml of water is added and boiled. It is then filtered and made into decoction. It is administered two times a day before food]

Both the trial drugs will be administered orally. The total drug therapy will be of three months duration.

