5.1 Study drug compliance/adherence

Research subject compliance with the assigned study drug will be recorded in the form during the periodical visits of the study participants.

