The eligible participants will be enrolled according to the inclusion criteria. The full details of the history and physical examination of the patient will be recorded as per the Proforma (Form 1 & 2) Clinical Assessment will be done on 0, 15, 30,45,60,75 and 90th days (Form 3). Laboratory investigations will be recorded as per the proforma (Form 4) before treatment (0 day), after treatment (at the end of 3rd 6th and 9th month).

6.2 Study drug procedures:

The study arm 1 will receive 100mg of drug with milk q.s after food at morning and night.

The study arm 2 will receive 60 ml of decoction before food at morning and night.

6.3 Follow-up procedures:

Follow ups in both arms will be carried out after 45th and 90th day after completion of 3 months treatment period.

6.4. Schedule of activities (Study table):

Type of study	Randomized, comparative, open labeled clinical study									
Phase	2									
Sample size	20 [without including drop outs, lama]									
Randomization	By appropriate method									
Study arms	Arm 1 => 10 subjects					Arm 2 => 10 subjects				
Intervention	xxx – 100 mg bid with milk after food					xxx- 60 ml bid before food				
Study period	6 months [3 months drug therapy + 3 months follow up]									
Visits		At initial visit (0)	I visit (15 th day)	II visit (30 th day)	III visit (45 th day)	IV visit (60 th day)	V visit (75 th day)	VI visit (90 th day)	Follow up 6 th month	Follow up 9 th month
Arm 1	10 subjects	Screening	Measuring IPSS and other Clinical data	Reporting ADR if any	Reporting ADR if any					
Laboratory investigations		USG,PSA test and other investigations						USG,PSA test and other investigations		
Arm2	10 subjects	Screening	Measuring IPSS and other Clinical data	Reporting ADR if any	Reporting ADR if any					
Data compilation	Data compiled for preparing monograph. Research article will be communicated after compiling the data.									

Safety and Effectiveness Assessments:

7.1 Safety assessment:

Blood and Urine examination will be done to evaluate the safety of the study drug. Laboratory investigations will be recorded as per the proforma (Form 4) before treatment (0 day), after treatment (at the end of 3rd 6th and 9th month).

7.2 Effectiveness assessment:

The IPSS, ultra sonogram study and test for PSA range will be done according to the proforma.

8. Adverse Event Reporting:

8.1 Adverse event definitions:

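### The only compliance diary shown is headed for after-meal dosing, which contradicts Arm 2's before-food regimen if Arm 2 is given it

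*Protocol*

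**What the plan says.** Section 5 says of the Arm 2 decoction: "It is administered two times a day before food". Section 6.2 repeats it: "The study arm 2 will receive 60 ml of decoction before food at morning and night". The study table in Section 6.4 gives the same timing. For Arm 1, the same three places specify twice-daily dosing with milk after food.

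On recording, Section 5.1 states: "Research subject compliance with the assigned study drug will be recorded in the form during the periodical visits of the study participants". The appended Drug Compliance Report Form for the 1st visit is marked "To be filled by study participant". Its dose columns are headed "Dose 1 (after breakfast)" and "Dose 2 (after dinner)", each followed by a column headed "Please enter the time". The participant ticks a dose taken and crosses a dose missed. Instruction d) adds: "Please return the unused medicine along with the drug compliance report duly filled". The form has 15 numbered rows and a blank line for the drug, and names no arm.

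**The concern.** Food timing is a stated part of each arm's regimen, and it is opposite in the two arms. A diary that prints after-meal timing at the head of both dose columns suits one arm only. If Arm 2 participants receive it, the sheet in front of them each day contradicts the regimen the protocol assigns.

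Two things would then be at stake. A participant who follows the printed heading takes the comparator at the wrong time relative to meals. A participant who correctly takes the decoction before breakfast has only an after-breakfast column to tick, so the record describes a departure that did not occur. Since Section 5.1 makes the form the compliance record, it could not be used to show that Arm 2 followed its assigned food timing.

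**Working it through.** No formula applies; the check sets one text against another.

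**Step 1. Compare the regimens with the diary headings.**

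| Source | Arm 1 | Arm 2 |
|---|---|---|
| Section 5 | after food | before food |
| Section 6.2 | after food | before food |
| Section 6.4 | after food | before food |
| Diary, dose 1 heading | agrees | conflicts |
| Diary, dose 2 heading | agrees | conflicts |

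The body text is consistent in 3 of 3 places for each arm. The diary conflicts with Arm 2 in 2 of 2 headings and with Arm 1 in 0 of 2. The error, if there is one, therefore lies in the diary and not in the regimen.

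**Step 2. Ask whether the diary is meant for both arms.** The protocol does not say. These points favour shared use:

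- The drug line is a blank to be filled in, like the subject number. Masked drug names elsewhere in the protocol appear as XXX, so this looks like a form field. A form for a single arm would hardly need it.
- The appended diary and IPSS sheet are labelled by visit, never by arm.
- Section 5.1 speaks of one form for whichever drug was assigned.
- The screening form covers both arms through a group A or B field.
- The 15 rows match the 15-day supply that Section 5.2.1 sets for each drug.

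**Step 3. Ask what the record could show in Arm 2.** Take a tick in the first dose column with a clock time beside it. It is compatible with a dose taken before breakfast as assigned and with a dose taken after breakfast as printed. The diary asks for no meal time, so the two cases cannot be separated. Whether the dose was taken at all is still readable from the tick or cross and from the returned medicine.

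**Step 4. Bound the number of entries concerned.** With 15 rows, 2 doses a day and the planned 10 Arm 2 participants, the form shown would hold 15 × 2 × 10 = 300 dose entries. If the diaries for all six 15-day periods up to day 90 carry the same headings, which is an assumption, the total is 6 × 300 = 1,800. These are entries with unclear food timing, not mistimed doses. The number of mistimed doses cannot be derived from the protocol.

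**The case against.** The strongest reply is that the contradiction is conditional. Nowhere does the protocol assign this diary to Arm 2, and since its headings fit Arm 1 exactly, it could be an Arm 1 specimen. The appended set is plainly incomplete: Form 4 is cited but not reproduced, and only the 1st-visit diary appears although six treatment visits are scheduled. An Arm 2 version may simply not be shown. The supports for shared use can each be questioned. The singular in Section 5.1 cannot mean one literal sheet, because later visits need further diaries. The group field on the screening form is absent from the diary, which could point to an arm-specific sheet. A blank drug line could also stand on a template for one arm.

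The consequences are also limited. Food timing is not an endpoint, and Section 5.2.3 has participants instructed at each review, so the printed heading is not their only guide.

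Much of this stands. Shared use remains an inference, and the effect is small. But the reply shows only that an unseen Arm 2 version is possible; nothing in the protocol mentions one. The missing group field decides little, since Forms II and III show none either. Instructions at review reduce the risk of mistimed doses but do not correct what the diary records. If a second version does exist, the form shown still lacks the label that would keep the two apart.

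**Conclusion.** The concern holds as a conditional inconsistency. The diary's headings contradict the Arm 2 regimen wherever the protocol states it, and use of the diary in both arms is the natural, though unstated, reading. The point is minor and confidence is medium, because everything beyond the text comparison depends on that reading. What would be lost is the ability to verify food timing in Arm 2, with some risk of prompting wrongly timed doses. No bias in IPSS is claimed, and sample size, alpha and power are unaffected.

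**What to change.** Before enrolment, do one of the following:

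- Give Arm 2 its own diary headed before breakfast and before dinner, and keep the present headings for Arm 1.
- Use one diary for both arms with neutral morning and night headings, which are the terms Section 6.2 uses for both arms, and add a before/after-food tick for each dose.

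If an Arm 2 version already exists, label each version with its arm. Carry the same change through the diaries for later visits. Neither arm's food timing needs to change.

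The cost is two altered column headings on one form, or one added tick per dose, with no extra visits, tests or participants. The change has to come before enrolment, because food timing not captured in a completed diary cannot be reliably recovered afterwards.
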